#### 4.1 Target CI DS Fitting Software

Study sites will be provided with a study laptop containing the Target CI DS fitting software to be used for the remote and in-office programming of electric and combined electric and acoustic modes of the Naída CI M DS sound processors. This software is functionally similar to the currently approved Target CI fitting software, providing utilities for changes in stimulation and fitting parameters.

All subjects enrolled at a participating study site will be fitted with the same study laptop.

#### 4.2 AB Remote DS App

Study sites will be provided with a smartphone containing the AB Remote DS app to be used for the remote programming of electric and combined electric and acoustic modes of Naída CI M DS sound processors. This software is functionally similar to the current

approved AB Remote app, providing additional utilities for an audiologist to change stimulation and fitting parameters through the app.				
All subjects enrolled at a participating study site will be fitted with				
the same smartphone.				
4.3 Naída CI M DS Sound Processors				
The study uses investigational Naída CI M sound processors				

## 5. Study Design and Justification

This pivotal study uses a prospective within-subjects repeated-measures design. A within-subject repeated-measures study design is appropriate as it accommodates the heterogeneity that characterizes hearing-impaired populations. Speech performance testing will be used to evaluate remote fitting of Naída CI M DS sound processors (investigational) as compared to in-office fitting of Naída CI M DS sound processors (control). Chronic exposure periods of 2-3 weeks between study visits will be used to evaluate the remote fitting in the subjects everyday hearing environment.

The study is designed as a multi-center study at up to 5 US centers to provide a more representative sample of the target population and make it easier to generalize the findings of the study. In addition, the 2-3 week chronic period between the in-office and remote fittings minimizes the possibility of a carry-over effect between fittings. The study will be considered completed when the last subject has completed their last visit.

[figure not shown]

Figure 2: Study Workflow

Adverse events (AEs) will be tracked and reported to the FDA according to the requirements of an IDE investigation until the study is closed. The AEs will be recorded and tracked between completion of the informed consent form and two weeks after the participant completes the study.

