- Subjects who meet inclusion and do not meet exclusion criteria are then fit with a Naída CI M DS sound processor in the audiologist's office. Unilateral ARH subjects will be fitted with an acoustic earhook and EO subjects will be fitted with a T-mic. Bilateral subjects meeting the ARH criteria will be fitted with an acoustic earhook in both ears. Fitting parameters on the Naída CI M DS sound processor should mimic the parameters on the subject's personal sound processor as closely as possible and be adjusted for comfort and sound quality as needed. Program settings will include two programs, one AutoSense OS program with and a second manually selected Calm situation program. This will be considered the in-office fitting.
- Acute speech perception in quiet is performed to confirm the in-office fitting on the Naída CI M DS sound processor.
- Adverse events and device observations are collected, as needed, and device accountability is performed.
- Following the visit, the subject will test the Naída CI M DS sound processor chronically for 2-3 weeks during their day-to-day activities.

#### 7.4.3 Visit 2

Visit 2 will occur 2-3 weeks after Visit 1.

- The visit will start at the audiologist's office with subjects completing a subjective outcome measures questionnaire.
- Chronic speech perception in quiet will be tested using AzBio sentences.
- In addition, the audiologist will introduce the remote fitting application to the subject and will pair the smartphone with the subject's Naída CI M DS sound processor. For the purposes of the study, a dedicated fitting smartphone will be used that is only used for remote fitting.

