- The subject will then move to the remote fitting location. The audiologist will initiate the remote fitting session through Target CI DS, and the subject will open the application on the remote fitting smartphone. Both parties will engage verbally to ensure audibility and visualization via smartphone video during the call. The audiologist then remotely connects to the subject's sound processor to begin the fitting session. The fitting will include measurement of impedances, measurement of electrode-specific neural response imaging (NRI), programming of M levels, and live speech stimulation to confirm acceptability of adjustments. Fittings for AHR subjects will include a review of acoustic and electric cutoff frequencies and gains at 65 dB. Additional adjustments may be made as needed to ensure comfort and clarity of the Map and to ensure acceptability of the fitting

during the subject's chronic wear period. The audiologist and subject will then confirm the completion of the fitting and both parties close their respective remote fitting session applications.

- Should technical issues occur during the remote fitting session, the audiologist will first try to mitigate the issues, for example by instructing the subject to turn off their outgoing video or to move to a different location in case of poor connection.
- ➤ The audiologist will re-schedule the remote fitting session should the remote app fitting not be completed because technical issues could not be mitigated during the session. Adverse events and/or device observations are collected and device accountability is performed, as needed.
- ➤ If remote fitting cannot be completed due to non-technical reasons (e.g. subject was not able to sufficiently communicate with the audiologist via the app), the subject will be exited from the study. Reasons for non-completion of the remote fitting will be documented. Adverse events and/or device observations are collected and device accountability is performed.
- After the remote fitting session is successfully completed, the subject will rejoin the audiologist in person for acute speech perception in quiet to confirm the remote fitting on the Naída CI M DS sound processor.
- In addition, the audiologist and the subject each will complete a custom remote fitting satisfaction questionnaire.
- Adverse events and device observations are collected and device accountability is performed, as needed.

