#### 8.1 Sample Size Justification

The primary efficacy endpoint is speech recognition on AzBio in quiet mode for remote fitting (Investigational) vs. in-office fitting (Control). Non-inferiority analyses will be based on paired t-tests looking at the differences in scores calculated using the Investigational speech scores minus the Control speech scores. A one-sided hypothesis test will be used with 0.025  $\alpha$  for the primary efficacy evaluation evaluating the following hypothesis:

$$H_0$$
:  $\mu_{\Delta}$  ≤ -10% versus  $H_1$ :  $\mu_{\Delta}$  > -10%

where  $\mu\Delta$  is the mean of the difference (remote fitting – in-office fitting) on the AzBio sentence test in quiet. A non-inferiority bound of 0.10 (10%) was selected for the AzBio test based on procedures used in previous studies

In addition, during validation of the AzBio sentence test, Spahr and colleagues showed that the 95% confidence intervals for average speech recognition for two-list administration approximated 10%. Based on these observations, performance falling outside of the sample confidence interval or greater than 10% would be considered a clinically significant difference (Spahr et al., 2012). Statistically significant test results that reject the null hypotheses, indicating that the means of the paired differences are greater

than -10 percentage points for AzBio in quiet mode, which will support that the Investigational condition is non-inferior to the Control condition. Previous data supported 6.24% SD for the primary efficacy endpoint. As shown in Table 1 below, with a sample size of 8 complete pairs there is 97% power to rule out a -10% null hypothesis supporting non-inferiority for a one-sided 2.5% test with statistical significance.

Table 1: Paired t-tests to reject the null hypotheses for non-inferiority and superiority

	Non- Inferiority
Test significance level, $\alpha$	0.025
1 or 2 sided test?	1
Null hypothesis mean difference, μο	-10
Alternative mean difference, μ Α	0
Paired SD, σ	6.24
Effect size, $\delta =  \mu_A - \mu_0  / \sigma$	1.603
Power (%)	97
N	8

These calculations are based on the T-distribution non-centrality factor as follows:

$$T_{n,NCF} = \frac{\sqrt{n} \left(\mu_{\Delta} - \mu_{0}\right)}{\sigma}$$

observed based on the non-centrality factor:

Power = 
$$T_{n-1}(T_{n-1}^{-1}(0.975), n-1, \delta = T_{n,NCF})$$

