#### 8.2.2 Supporting Data

The following supporting data will also be evaluated using descriptive statistics:

- subjective outcome measures
- custom subject remote fitting satisfaction questionnaire
- custom audiologist remote fitting satisfaction questionnaire
- subject reimbursement questionnaire
- acute speech perception data
- in-office fitting vs remote fitting duration
- psychophysical data
- duration of in-office vs remote fitting.

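### The in-office and remote fitting sessions follow different listed steps and the remote session's starting map is not stated, so the duration and psychophysical comparisons are not like for like and the wear period does not remove carry-over of the map.

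*Combined protocol and SAP*

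**What the plan says.** Section 5 defends the fixed sequence (in-office fitting at Visit 1, remote fitting at Visit 2) on the ground that "the 2-3 week chronic period between the in-office and remote fittings minimizes the possibility of a carry-over effect between fittings".

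Section 7.4.2 describes the in-office fitting. Its parameters "should mimic the parameters on the subject's personal sound processor as closely as possible and be adjusted for comfort and sound quality as needed", and two programs are set up, one AutoSense OS and one manually selected Calm situation program. The subject then wears that processor for 2-3 weeks.

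Section 7.4.3 pairs the study smartphone with the same processor, and the audiologist connects to it to begin the remote fitting. The required steps are impedances, NRI, programming of M levels and live speech, plus a review of acoustic and electric cutoff frequencies and gains for ARH subjects. Beyond these, "Additional adjustments may be made as needed to ensure comfort and clarity of the Map".

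Section 8.2.2 lists "in-office fitting vs remote fitting duration" and psychophysical data among the supporting data, and section 8 frames both as remote against in-office. Sections 8.2.2 and 8.2.5 make these analyses descriptive. Section 3 gives the intended use of the remote option as follow-up fittings.

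**The concern.** There are two separate problems.

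The first is comparability. Visit 1 is a first set-up on a new processor that copies existing settings. Visit 2 is a measured refit. A difference in duration between them mixes the route (remote or office) with the task. Psychophysical values can be compared only if both sessions measure the same things, and 7.4.2 lists none of the measurements in 7.4.3.

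The second is what the primary difference can show. A wear period limits carry-over when the earlier condition is absent during it. Here the earlier condition is what is worn. If the remote session ends close to the in-office settings, the Visit 3 score is largely a second score of the in-office map, and the paired difference moves towards zero, which is the direction of success in a non-inferiority test. Subjects have at least 6 months of implant experience, so near-coincident maps are plausible. Nothing in the text requires the map to be saved before and after the session or the change to be reported, and Table 2 has no deviation for fitting content. This does not depend on visit order: it would remain with no practice or period effect.

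**Working it through.** **The two sessions side by side**

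| Item | In-office (7.4.2) | Remote (7.4.3) |
|---|---|---|
| Starting point | Personal processor's parameters | Not stated; same processor, no reset described |
| Impedances, NRI | Not listed | Required |
| M-level programming | Not listed as a step | Required |
| Live speech | Not listed | Required |
| Two-program set-up | Required | Not listed |
| Acoustic review (ARH) | Earhook fitted; review not listed | Required |
| Saved or reported map change | Not stated | Not stated |

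Section 7.2.2 says psychophysical data come from the fitting sessions, in the plural, so the plan seems to expect them at Visit 1 as well. The step list in 7.4.2 does not match, and the two sections need to be reconciled.

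**The plan's own power figure**

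Inputs from section 8.1: "A one-sided hypothesis test will be used with 0.025" as α; "A non-inferiority bound of 0.10 (10%) was selected for the AzBio test"; Table 1 gives "Alternative mean difference" as 0; "Previous data supported 6.24% SD for the primary efficacy endpoint"; n = 8 complete pairs.

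- Effect size = 10 / 6.24 = 1.603, as in Table 1.
- Non-centrality = √8 × 10 / 6.24 = 4.53, with 7 degrees of freedom.
- Power = 97.1% (plan: 97%). With 12 pairs it is 99.9%.

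The power calculation reproduces and is not in dispute.

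**What the test requires**

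Success needs the lower confidence bound to exceed -10. The half-width is t(0.975, n-1) × 6.24 / √n.

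- n = 8: 2.365 × 6.24 / √8 = 5.22, so the observed mean must exceed -10 + 5.22 = -4.78.
- n = 12: 2.201 × 6.24 / √12 = 3.96, so the observed mean must exceed -10 + 3.96 = -6.04.

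**How much could a retained map matter?**

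The documents give no figure for retention, so both models below rest on assumptions and serve only to show a range.

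*Model A, mixture.* A fraction f of remote sessions leaves the map effectively unchanged (true difference 0). The rest truly lose 15 points. The noise SD is 6.24. The expected mean is (1 - f) × (-15), and the SD of differences is √(6.24² + f(1 - f) × 15²). The chance of declaring non-inferiority is by simulation.

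| f | Expected mean | SD | n = 8 | n = 12 |
|---|---|---|---|---|
| 33% | -10.0 | 9.4 | 2% | 2% |
| 40% | -9.0 | 9.6 | 4% | 4% |
| 50% | -7.5 | 9.8 | 9% | 12% |
| 75% | -3.75 | 9.0 | about 41% | 58% |

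*Model B, uniform shrinkage.* Every subject keeps a share f of the in-office map, and an independent remote fitting would be exactly 10 points worse. The mean is (1 - f) × (-10), and the SD stays at 6.24.

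| f | Mean | n = 8 | n = 12 |
|---|---|---|---|
| 0 | -10.0 | 2.5% | 2.5% |
| 25% | -7.5 | 16% | 24% |
| 50% | -5.0 | 50% | 72% |
| 75% | -2.5 | 83% | 97% |

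At f = 50% the chance of declaring non-inferiority runs from 9% to 72%, depending on the model, the assumed loss and the number of pairs. The documents do not allow a choice between the models.

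**The case against.** Four counter-arguments carry weight.

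- **The starting map is unstated, not known.** A reader might infer that the remote session edits the in-office map still on the processor. The same processor and the absence of a reset step suggest it, but no section says so. The workflow figure and the case report forms are not in the available text and may say more.
- **A session that does nothing is off-protocol.** M-level programming is required at Visit 2; only changes beyond the listed steps are discretionary. If M levels set remotely agree with those from the office, that is a valid remote fitting. What remains is that the plan cannot separate agreement from inaction.
- **Starting from an existing map may be the right test.** Sections 3 and 11.1 intend the remote option for follow-up programming. Forcing the remote session to open from an older file would change the question being asked.
- **The plan already has a partial safeguard.** Section 8.2.3 tabulates individual decrements against an 8.9-point critical difference. With a true 15-point loss and SD 6.24, about Φ((15 - 8.9) / 6.24) = 84% of affected subjects would be flagged. That would reveal harm where the map was changed. It would not show whose map was changed.

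It is also fair that the duration and psychophysical comparisons carry no hypothesis or success criterion.

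**Conclusion.** The point holds as a matter of comparability and interpretation. The listed steps differ, so the duration and psychophysical comparisons as planned mix route with task. The in-office fitting is worn throughout the interval that section 5 relies on, so that interval does not remove carry-over of the map. With no stated starting map and no required record of change, similar scores at Visits 2 and 3 have two readings: remote fitting works as well, or little was refitted.

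A reader might go further and infer that the primary test is invalid or that its false-positive rate is known to be inflated. The documents do not support that. How often a map is largely retained is unknown, the rates above depend on assumed retention and assumed loss, and under the mixture model the effect is modest until well over half the sessions leave the map unchanged. The sample size and the stated 97% power are unaffected.

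**What to change.** 1. Use one common list of measurements in 7.4.2 and 7.4.3, and compare duration on those steps only. Alternatively, report duration step by step with program set-up shown separately. Which measurements go on the list is for the sponsor and investigators to settle; the two sections need to agree.
2. State the starting map of each session. Save the map before and after each session, and report the per-subject change in M levels (and in acoustic gains for ARH subjects) descriptively beside the primary result. Do not add a re-test in subjects whose map changed: that would select on a post-fitting variable in a sample that may have only 8 EO pairs.
3. Reword the section 5 sentence so that it no longer claims the wear period minimises carry-over of the fitting itself.

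The cost is a few more minutes of non-invasive measurement at Visit 1, one extra descriptive table and protocol wording. No added visits or subjects are needed, and the primary analysis does not change.

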## 6. Objectives

The primary efficacy objective is to demonstrate non-inferiority of speech recognition in quiet after remote fitting as compared to speech recognition in quiet after in-office fitting.

## 7. Study Protocol

### 7.1 Subject Population and Selection Criteria

Advanced Bionics expects to fit up to 17 HiResolution Bionic Ear system users 13 years or older via remote fitting in this clinical study across up to 5 study sites in the United States. This study population is expected to be representative of the target population for remote fitting. An individual is considered to be enrolled as a study participant once the informed consent document has been signed and dated. It is anticipated that more than 17 subjects will be enrolled in the study as some may not meet the inclusion / exclusion criteria. Prior to recruitment, written approval of the investigational plan and informed consent form will be obtained from the FDA and associated participating study center Institutional Review Boards (IRB). Study participants are required to meet the study inclusion criteria as determined by the Principal Investigator. Depending on the outcome of their audiogram, eligible subjects will be enrolled for aidable residual hearing (ARH) fitting with an acoustic earhook. Unilaterally implanted subjects not meeting ARH fitting criteria will be enrolled for electric only (EO) fitting. Bilaterally implanted subjects meeting ARH criteria only in one ear will be screen failed.

Enrollment in the study is expected to occur over a period of approximately 6 months. Subjects meeting inclusion criteria will participate in 3 study visits over approximately 4-6 weeks.

#### 7.1.1 Inclusion Criteria All Subjects

- Ability to provide Informed Consent/Assent
- 13 years of age or older
- Unilateral or bilateral user of a HiResolution™ Bionic Ear System (HiRes 90K™, HiRes 90K™ Advantage, HiRes™ Ultra, HiRes™ Ultra 3D)
- Minimum of 6 months of CI experience with a minimum of 1 month experience with a Naída CI or Sky CI sound processor
- At least moderate open-set speech recognition abilities (defined as speech in quiet score ≥ 60% as assessed at Visit 1)
- Minimum average score ≥ 3 on the Mobile Device Proficiency Questionnaire (MDPQ-16)
- English language proficiency as determined by the Investigator
- Willingness to use a BTE sound processor for the duration of the study

#### 7.1.2 Inclusion Criteria Specific to ARH Group

- Residual low frequency hearing sensitivity (pure tone average of < 70 dB HL for 125, 250, and 500 Hz) and a severe-to-profound high-frequency sensorineural hearing loss (pure tone average of ≥ 70 dB HL for 1,000, 2,000, 3000, 4,000, and 8,000 Hz) in the implanted ear for unilaterally implanted subjects and in both ears for bilaterally implanted subjects
- Willingness to use an in-canal acoustic earhook for the duration of the study

#### 7.1.3 Exclusion Criteria All Subjects

Clinical presentation indicative of potential device malfunction

- Unrealistic expectations regarding potential benefits, risks and limitations of the investigational device as determined by the Investigator
- Unwillingness or inability of subject to comply with all investigational requirements as determined by the Investigator

### 7.2 Study Endpoints

## 7.2.1 Efficacy

The purpose of the proposed study is to evaluate speech performance efficacy objectives. The primary efficacy endpoints are chronic remote fitting AzBio sentence scores in quiet at Visit 3 as compared to chronic in-office AzBio sentence scores in quiet at Visit 2.

## 7.2.2 Supporting data

In addition to acute speech performance, psychophysical data and fitting durations, information from subjective questionnaires will be collected as supporting data:

- Information regarding study participants experience during fitting sessions will be collected via a Subject Remote Fitting Satisfaction Questionnaire.
- Information regarding study participants listening experience during the chronic periods will be collected via a SSQ-12 questionnaire.
- Information regarding study participants reimbursement situation will be collected via a Reimbursement Questionnaire.
- Information regarding investigators' experience during fitting sessions will be collected via an Audiologist Remote Fitting Satisfaction Questionnaire.
- Information regarding acute speech perception will be collected in form of AzBio sentence scores collected immediately after in-office and remote fitting, respectively.
- Information regarding duration of in-office and remote fitting durations will be collected during the fitting sessions.
- Information regarding psychophysical data will be collected during the fitting sessions.

#### 7.2.3 **Safety**

Adverse event data will be collected and evaluated during the study to ensure that the safety of patients is maintained as per requirements of an IDE and respective center Institutional Review Board guidelines for reporting. The primary safety endpoint is the absence of unanticipated adverse device effects related to remote fitting.

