#### 7.3.1 Audiometric Measures:

Unaided air conduction hearing thresholds (in dB HL) will be measured for the implanted ear(s) using the centers calibrated audiometer and standard audiometric technique for pure-tone air conduction testing.

Unaided air conduction thresholds using insert earphones at octave and inter-octave frequencies will be obtained (125, 250, 500, 1000, 2000, 3000, 4000 and 8000 Hz).

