#### 7.4 Study Visits and Visit Windows

#### 7.4.1 Schedule of Events

Procedure	Visit 1	Visit 2	Visit 3
Informed Consent/Assent	~		-
Demographics & Audiological History	Y		
Mobile Device Proficiency Questionnaire	>		
Reimbursement Questionnaire	>		
Audiometric Thresholds	Y		
AzBio in Quiet, Personal Sound Processor	>		
Confirmation of Eligibility	Y		
Naída CI M DS Sound Processor In-Office Fitting	>		
Naída CI M DS Sound Processor Remote Fitting via Smart Phone App		•	
Acute AzBio in Quiet, Naída CI M DS Sound Processor	Y	>	
Chronic AzBio in Quiet, Naída CI M DS Sound Processor		>	>
Subjective Outcome Measure Questionnaire (SSQ-12)		>	>
Custom Subject Remote Fitting Satisfaction Questionnaire		✓ &	
Custom Audiologist Remote Fitting Satisfaction Questionnaire		✓ &	
Adverse Event Assessment	>	>	>
Device Accountability	~	~	>
& Only if remarks fitting was accomplying appealated			

& Only if remote fitting was successfully completed

#### 7.4.2 Visit 1

This visit is performed at the audiologist's office.

- After informed consent/assent, subject's demographics and hearing history will be captured.
- Subjects' technical competency will be determined using the Mobile Device Proficiency (MDPQ-16) questionnaire and subjects will complete a Reimbursement Questionnaire.
- Speech perception in quiet will be tested using the subject's personal sound processor to determine eligibility for the study.
- Audiometric thresholds are used to determine whether subjects are considered to have aidable residual hearing (ARH). Subjects not meeting the ARH criteria will be fitted under the electric-only criteria (EO). Audiometric thresholds will be determined for the implanted ear only for unilaterally implanted subjects and for both ears individually for bilaterally implanted subjects.
  - Bilateral subjects meeting the ARH inclusion criteria in both ears will be enrolled in the ARH group. Bilateral subjects meeting ARH criteria in only one ear will be screen failed.

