#### 9.3 Anticipated Adverse Events

The risks associated with the investigational products include but are not limited to:

- There is a possibility that speech and environmental sounds may sound different or louder than what the subjects are accustomed to hearing or that subjects may not like the sound quality of the study sound processor used in the study. This risk occurs with all changes to sound-processing, and subjects should be advised of this possibility. If a subject cannot tolerate using the study sound processor or does not like the sound quality, they can return to using their own sound processor with their baseline programming. In this event, the subject will be withdrawn from the study.
- Subjects may experience some overly loud sounds that result in discomfort. If such loud sounds occur, they can be stopped immediately by removing the headpiece and/or the entire external device.
- Subjects may experience neural tissue damage in the event of chronic overstimulation.
- There is risk of facial nerve stimulation. This risk can be mitigated through reprogramming of the device.
- Subjects may experience intermittent sound or short-term loss of functionality while
  wearing the device or while being programmed. The intermittency can be eliminated by
  changing the headpiece, reprogramming the sound processor, or exchanging the sound
  processor.
- Subjects may have permanent residual acoustic or natural hearing damage due to excessive acoustic power.
- Subjects may experience skin or tissue irritation because of the device materials or the equipment may overheat or otherwise malfunction, causing tissue damage.
- Subjects will be exposed to small parts that pose a choking hazard. Care should be taken to avoid choking and the outcomes of choking, such as endoscopic surgery or death.
- Exposure to electromagnetic emissions from the device (external sound processor, internal device) may adversely interfere with other electronic medical devices
- Subjects should only use accessories compatible or designed for the study sound processor (such as the battery chargers) in order to avoid electric shock.
- Static electricity can potentially damage sensitive electronic components such as the ones used in the cochlear implant system.

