A complete listing of the risks can be found in Appendix A; all risks listed are considered anticipated Adverse Events. Risks are minimized by device safety testing but cannot be completely eliminated. At any time, subjects may discontinue use of the study sound processor, and return to using their own sound processor and baseline program. If subjects stop using the study sound processor during the study, they will be withdrawn from the study.

In all case, the event(s) will be recorded and the incidence of such events reported as part of the results analysis.

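### Does the plan need repeat hearing thresholds before it can report safety in the residual-hearing (ARH) group?

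*Combined protocol and SAP*

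**What the plan says.** Section 7.2.3 sets the safety endpoint: "The primary safety endpoint is the absence of unanticipated adverse device effects related to remote fitting". Its source is adverse event collection.

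Section 9.3 lists, among the risks of the investigational products, "Subjects may have permanent residual acoustic or natural hearing damage due to excessive acoustic power", and adds that "all risks listed are considered anticipated Adverse Events".

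The acoustic mode is within the tested procedure. Section 4.2 describes the app as serving "remote programming of electric and combined electric and acoustic modes", and section 7.4.3 says of the remote session: "Fittings for AHR subjects will include a review of acoustic and electric cutoff frequencies and gains at 65 dB". Further adjustments are allowed. An inclusion criterion for the ARH group (section 7.1.2) is "Willingness to use an in-canal acoustic earhook for the duration of the study".

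On audiometry, section 7.3.1 says "Unaided air conduction thresholds using insert earphones at octave and inter-octave frequencies will be obtained". The synopsis, the schedule in section 7.4.1 and the visit descriptions in sections 7.4.2 to 7.4.4 agree that this happens at Visit 1 only. Section 7.4.2 gives the purpose as deciding whether a subject is ARH or electric only.

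Section 8.1 plans 5 ARH subjects, analysed descriptively, and gives 16.2% as the one-sided 95% upper bound when no events occur in 17 subjects.

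**The concern.** The plan names a permanent harm, exposes a group to the mode that could cause it, takes a baseline audiogram and never repeats it. Section 3 aims to demonstrate safety, and section 8.1 enrols the ARH group to provide confirmatory data on the combined electric and acoustic mode. A report of no hearing damage could mean that no shift occurred or that nobody noticed one. A later statistical analysis plan can add tables but cannot recover a measurement that was never taken.

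Two further points add to the worry. Because the harm is listed as anticipated, a reported case would normally not count against the endpoint unless its severity or frequency went beyond what had been identified (section 9.1.3). And the 16.2% bound uses 17 subjects, while at most 5 have the acoustic exposure. A reader could take it as reassurance about hearing damage.

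**Working it through.** **1. The plan's own bound.** For zero events in n subjects, the one-sided 95% exact upper bound is 1 − 0.05^(1/n).

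- n = 17 (section 8.1): 1 − 0.05^(1/17) = 16.16%, matching the stated 16.2%.
- n = 5 (planned ARH group): 1 − 0.05^(1/5) = 45.1%.
- n = 4: 52.7%. n = 3: 63.2%.

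Section 8.1 offers 16.2% for complication rates in general, in all 17 subjects. It does not apply the figure to hearing damage, so there is no wrong number to correct.

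**2. What complete measurement would add.** Let p be the true rate of the harm and r the share of cases that come to light. The chance of recording at least one case in 5 is 1 − (1 − p·r)^5. The documents give neither p nor r, so both are assumptions. Take r = 1 if every case is measured and r = 0.5 if half are noticed and reported.

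| Assumed true rate | r = 1 | r = 0.5 | Difference (points, rounded) |
|---|---|---|---|
| 1% | 4.9% | 2.5% | 2 |
| 5% | 22.6% | 11.9% | 11 |
| 10% | 41.0% | 22.6% | 18 |
| 20% | 67.2% | 41.0% | 26 |
| 30% | 83.2% | 55.6% | 28 |

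The gain is sizeable only if the harm is common. The r = 1 column also assumes error-free audiometry and an agreed definition of a case, and the plan has no shift criterion.

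**3. What a zero result would support.** With every case measured, zero in 5 bounds the rate at 45.1%. With half noticed, it bounds the true rate at 45.07% / 0.5 = 90.1%. Measurement halves the bound in this example, but neither figure supports a safety claim for this harm.

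**4. Attribution.** Every subject has the in-office fitting first and the remote fitting second. There is no concurrent control, and the earhook is worn in both periods. A change between Visits 2 and 3 could not be assigned to remote fitting, which is what the endpoint concerns.

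**5. A ready-made criterion?** The only hearing limit in the plan is the low-frequency average below 70 dB HL in section 7.1.2, which is an eligibility rule. An ear at 30 dB could lose 35 dB, reach 65 dB and still qualify. An ear at 69 dB would fail after a 1 dB change. It cannot serve as a measure of harm.

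**6. What already catches the event.**

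- Adverse events are assessed at Visits 1, 2 and 3 (section 7.4.1) by trained audiologists (section 4), who could suspect a loss and order an unscheduled audiogram.
- Recording runs to two weeks after the last visit (section 9).
- A serious deterioration that leaves a lasting loss of a bodily function meets the serious event definition (section 9.1.1), with immediate reporting and follow-up (section 9.2).
- Subjects discontinued for a device-related event are followed (section 7.5).
- Section 13.1 asks for no special follow-up because subjects go back to their personal processor.

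**7. Cost.** 5 subjects × 2 visits = 10 extra audiometry sessions at most, plus a listing.

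**The case for a change.** The strongest reply is that 10 sessions on an audiometer each site must already have is a small price when the harm is permanent and on the sponsor's own list. A descriptive listing needs no power and would suit the descriptive purpose of the ARH group. The earhooks are commercially approved (section 4), but the software that sets the acoustic mode is investigational. Without thresholds, a lower Visit 3 AzBio score in an ARH subject cannot be split into a fitting effect and a change in residual hearing.

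Much of this stands. No scheduled measurement can detect a threshold shift, and neither AzBio nor the SSQ-12 measures unaided hearing. A sponsor could reasonably choose to repeat the audiogram. But the listing would have no agreed shift criterion and could not separate remote fitting from the order of the periods. The AzBio point has less force: hearing lost through the remote fitting would belong to the effect that the paired difference is meant to capture, so the primary comparison does not need the split.

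It is also unclear why this listed risk alone should need a scheduled test. Section 9.3 also lists neural tissue damage, facial nerve stimulation and choking, and these too are left to adverse event reporting.

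**Conclusion.** No change to the plan is needed. The observation is correct: residual-hearing damage is a named risk, the acoustic mode is part of remote fitting, and no threshold is scheduled after Visit 1. Detection depends on a subject or audiologist noticing a loss within the adverse event process. That is a fair trade-off in a group of at most 5, studied descriptively and in fixed order. Repeat audiometry would add a procedure of debatable worth and correct no wrong figure or rule.

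The limit on interpretation is real: no reported cases in the ARH group would not establish that residual hearing was preserved, and zero in 5 has an upper bound of 45.1% even if every case were found. An analyst can say so in the clinical study report without altering the design.

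This conclusion assumes that adverse event assessment at each visit is carried out as written. Appendix A, the remote-fitting risk list that follows section 12.4 and the case report forms are not in the public text, so any further control of acoustic output could not be checked. The detection probabilities rest on assumed rates and reporting shares and show only how the gain depends on them.
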